
orthotics direct report and/or subject self reportself-report and /or medical record review. Typical standard care will include providing a customized prosthetic socket by casting the individual's residual limb and utilizing various socket and liner materials to provide optimal residual limb to prosthesis interface. This will also include modifications by reducing excessive pressure points, incorporating additional padding and utilizing a variety of prosthetic components and alignment techniques to best accommodate each individual. In addition, many patients may have already received interventions such as skin grafting, muscle flaps, residual limb reconstructive surgeries, neuroma injections or excision to best achieve a functional and non-painful residual limb. When defining "maximal attempts to refit the prosthesis" we define it as patients who have been unsuccessful in achieving a functional and comfortable prosthetic socket despite a minimum of 3 months of working with a prosthetist. This will include a minimum of at least 5 different socket adjustments. "Changes in the design of the prosthesis", will include re-casting the residual limb, providing pressure relieves within the socket, changing the alignment of the prosthetic components to alter ground reactive forces, and adding padding to pressure sensitive areas. The approximate range of the defect volumes can be small (5-10cc), or as much as 300cc if the defect is a very local soft tissue deficiency over a pressure point. The volume of the defect correlates with moderate or severe intolerability of the prosthesis. The following evaluations will be conducted by or under the supervision of a certified prosthetist and/or occupational or physical therapist. For the Orthotics and Prosthetics evaluation all study participants will be assessed pre and post the procedure to determine the functional changes related to prosthetics ambulation and residual limb health and structure. All participants will be asked to complete the all of or a subset of the following questionnaires and assessments prior to the surgical procedure (Screening) and after the surgical procedure.a. "Prosthetics Evaluation Questionnaire" (PEQ) is a self-report questionnaire containing 54 questions organized into nine functional domains related to prosthesis-related changes in quality of life. The PEQ was developed to fill the need for a comprehensive self-report instrument for individuals with lower limb loss. (143- Legro 1998). Psychometric analysis supported the reliability and validity of the PEQ for evaluating the function of the prosthesis and the major health related quality of life domains. The PEQ is estimated to take 15 minutes or less to complete. b. The 6minute walk test (6MWT) is a reliable measure of functional capacity, involves a moderate degree of exercise intensity, and is related to a moderate degree to postural control abilities in persons with lower-limb amputations. (144 - Lin S-J, Bose NH, 2007). This 6MWT is estimated to take 20 minutes or less to complete, including the baseline rest period, set-up, and 6 minutes of continuous walking. c. The Amputee Mobility Predictor (AMP) is 21 item instrument designed to assess determinants of the lower-limb amputee ability to ambulate. The AMP is estimated to take approximately 15 minutes or less to complete. d. Lower Extremity Functional Scale (LEFS) is a self-reported questionnaire containing 20 questions about a person's ability to perform everyday tasks. The LEFS is anticipated to take approximately 10 minutes or less to complete.e. The Disabilities of the Arm, Shoulder, and Hand (DASH) outcome Measure is a 30-item, self-report questionnaire designed to

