Visit 2 and/or 3 PO only the subject will be evaluated by the Prosthetic /Orthotics/Occupational therapy team (limited physical exam) in conjunction with the PI to determine weight bearing readiness as well as readiness to obtain a standard of care check socket by their primary prosthetist. The participant's prosthetic device (including check socket and or permanent socket) and any other assistive devices used will be fitted as part of their routine standard of care and will only be documented that the visit happened. The subject will be instructed NOT to wear the prosthetic sockets until seen by research team and/or clearance received to utilize any new prosthetic devices which is anticipated to occur at approximately POV3 or POV4. The subject may be asked to attend an interim visit at 4-5 months PO, if the check socket and permanent socket fabrication fall out of the PO visit 2-3 range. At Post op visit 4 (6 months post op), POV5 (month 12) and POV6 (month 24) the prosthetist and therapist will implement the assessments and select the appropriate assessments based on the participant's functional status, amputation site(s), and assistive technology used. The following assessments are dependent upon the location (upper verses lower extremity) and may or may not be completed depending upon the site of interest. a. Prosthetics Evaluation Questionnaire (PEQ) is a self-report questionnaire containing 54 questions organized into nine functional domains related to prosthesis-related changes in quality of life. The PEQ was developed to fill the need for a comprehensive self-report instrument for individuals with lower limb loss. (Legro 1998). Psychometric analysis supported the reliability and validity of the PEQ for evaluating the function of the prosthesis and the major health related quality of life domains. The PEQ is estimated to take 15 minutes or less to complete. b. The 6 Minute Walk Test (6MWT) is a reliable measure of functional capacity, involves a moderate degree of exercise intensity, and is related to a moderate degree to postural control abilities in persons with lower-limb amputations. (Lin S-J, Bose NH, 2007). This 6MWT is estimated to take 20 minutes or less to complete, including the baseline rest period, set-up, and 6 minutes of continuous walking. This test will not be conducted if the participant is not able to functionally ambulate with use of prosthetic device. c. The Amputee Mobility Predictor (AMP) is a 21 item instrument designed to assess determinants of the lower-limb amputee ability to ambulate. The AMP is estimated to take approximately 15 minutes or less to complete. d. Lower Extremity Functional Scale (LEFS) is a self-reported questionnaire containing 20 questions about a person's ability to perform everyday tasks. The LEFS is anticipated to take approximately 10 minutes or less to complete. e. The Disabilities of the Arm, Shoulder, and Hand (DASH) outcome Measure is a 30-item, self-report questionnaire designed to

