Pain and Serial computed tomography imaging will be performed and measured as parametric data sets before fat grafting and afterwards at various time points using a paired t-test model. Repeated measures analysis of variance will be used to evaluate change over time in all outcome measures. Using standard conventions of alpha=0.05 and beta=0.8, an enrollment of thirty patients may provide sufficient power to detect a Cohen's effect size of about 0.9 which is anticipated to be adequate for detecting clinically meaningful differences in the volume of soft tissue. A composite functional score will be constructed from the prosthetics and occupational therapy evaluations and compared between study groups. The details of this analysis, including which evaluations will be included in the score and relative weight, can be best determined as the study progresses and initial data sets are acquired. Additionally, each assessment score from the specific tests will also be considered individually for comparison.

[reviewer notes-]

Section 2 - Research Design and Methods

2.19

Will this research be conducted in (a) a foreign country and/or (b) at a site (e.g., Navajo Nation) where the cultural background of the subject population differs substantially from that of Pittsburgh and its surrounding communities?* No

Note that copies of training records, licenses, certificates should be maintained in the study regulatory binder and are subject to audit by the Research Conduct and Compliance Office (RCCO).

Section: Section 2 - Research Design and Methods

In addition, individuals planning to conduct human subject research outside the United States must complete an optional module on the CITI training website: International Studies. Click [here](#) to access the instruction sheet for accessing optional CITI modules.

- 2.19.1 Address the following for each of the foreign/culturally different sites where this research will be conducted:
- Name of site
 - Name of authorized individual (e.g., IRB Chair) from the local IRB or other human subject protections entity that is responsible for the review and approval of the project; upload approval letter with an English translation, if applicable
 - Name and qualifications of the site collaborator responsible for the conduct of the research (e.g., site PI)
 - The anticipated number of subjects that will be enrolled at that site
 - If Federally funded, provide the Federalwide Assurance number (FWA) assigned to the site *

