site] compared to a lower extremity amputation site [high weight bearing site]. Therefore we have provided an adequate number of potential subjects to be screened and enrolled to study pain at the amputation site with these different treatments. For this study, 70 potential subjects will be screened and enrolled with a goal of 30 subjects to undergo the operative autologous fat grafting procedure. Each subject will be assigned to a specific randomization block based on whether they have an upper or lower extremity amputation. Each randomization block will have six (6) subjects. There will be a computer generated randomization assignment for each subject to receive the surgical intervention that will be either fat grafting alone or fat grafting with stromal vascular fraction cells. A randomization table will be generated using a software program [Research Randomizer, Version 3.0]. This will allow for statistical examination between the two different treatments within each randomization block (3 subjects receive fat graft and 3 subjects receive fat graft with stromal vascular fractions). There will be five (5) randomization blocks for a total of thirty (30) subjects. Therefore based on the prevalence of subjects who have either the upper and lower extremity amputation, there may be a range from one (1) to five (5) randomization blocks for one of the treatment groups. We expect that there will be a higher number of lower extremity amputees who call-in or are referred for screening. The proposed block randomization scheme will be flexible to handle various numbers of either upper or lower extremity amputations as well preserve the statistical rigor for testing.

[reviewer notes-]

Section 3.0 - Human Subjects

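### The composite functional score has no rule for scoring upper- and lower-limb patients together and no limb term, and its tests may be re-selected after surgery according to functional status

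*Combined protocol and SAP*

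**What the plan says.** Section 2.18 states that "A composite functional score will be constructed from the prosthetics and occupational therapy evaluations and compared between study groups". It adds that "which evaluations will be included in the score and relative weight, can be best determined as the study progresses", and that "each assessment score from the specific tests will also be considered individually for comparison". It has no limb-level scoring rule and no limb term.

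Section 2.7, item 5, lists evaluations a to h and says they are "dependent upon the location (upper verses lower extremity) and may or may not be completed depending upon the site of interest". At months 6, 12 and 24 the prosthetist and therapist choose tests by functional status, amputation site and assistive technology. The walk test is skipped for a patient who cannot walk functionally with the prosthesis. At screening (Section 2.5.1, item 10), "All participants will be asked to complete the all of or a subset of the following questionnaires and assessments".

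Both limb levels are eligible (Section 3.13, criterion 7). Section 3.12 randomises 30 patients in five limb-specific blocks of six, 3:3, and leaves the mix open: "there may be a range from one (1) to five (5) randomization blocks for one of the treatment groups". In context the groups meant there are the limb groups. More lower-limb patients are expected, but no figure is given. Section 2.3 describes the trial as non-blinded.

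**The concern.** The composite pools tests that do not all apply to every patient. PEQ is introduced as a "comprehensive self-report instrument for individuals with lower limb loss" and the walk test is justified by its relation to "postural control abilities in persons with lower-limb amputations", while DASH is an upper-limb measure. Two patients in the same arm can thus be scored on largely different tests, with nothing said about how the scores are made comparable.

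The tests may also differ within one patient. Selection at screening is loose, and selection at follow-up depends on functional status, which is what the composite is meant to measure. Prosthesis tolerance is a primary outcome in Section 2.17, assessed partly by the prosthetics team, so the functional comparison matters. Fixing only the weights in advance would leave both problems in place.

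**Working it through.** **1. Evaluations by limb (Section 2.7, item 5, a to h)**

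| Evaluation | Limb, as described |
|---|---|
| PEQ | Lower |
| 6-minute walk test (6MWT) | Lower |
| AMP | Lower |
| LEFS | Lower (by name) |
| DASH | Upper |
| FMA | Either |
| Prosthetic Device Use History | Either; no numeric score stated |
| Physical examination | Either; no numeric score stated |

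Four of eight are lower-limb, one is upper-limb and three are common. Among the six named scales, a lower-limb patient can have five and an upper-limb patient two, with FMA shared.

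**2. Effect of changing the test set**

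Take a lower-limb patient scored as the mean standardised change over the five applicable scales. Suppose walking worsens by x SD and the other four scales do not change.

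- Walk test retained: score = (0 + 0 + 0 + 0 − x)/5 = −x/5.
- Walk test omitted because the patient can no longer walk functionally: score = 0/4 = 0.

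The deterioration disappears. If such omissions differ between arms, the arm difference is biased, and balanced randomisation does not remove this because selection happens after treatment.

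**3. The plan's own sample-size figure**

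Section 2.18 gives alpha 0.05, power 0.80 (printed as beta), Cohen's d about 0.9 and 30 patients, for soft-tissue volume. Sidedness is not stated. By the normal approximation, n per arm = 2(z_alpha + z_power)²/d².

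- One-sided: 2(1.645 + 0.842)²/0.81 = 15.3, so 16 per arm, 32 in total. At 15 per arm, power is 79.4% (77.6% by the t-test).
- Two-sided: 2(1.960 + 0.842)²/0.81 = 19.4, so 20 per arm (21 by the t-test). At 15 per arm, power is 69.3% (66.3% by the t-test).

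The figure is reproduced, within two patients, only as a one-sided test.

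**4. Illustration: upper-limb patients left unscored**

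Assumptions: d = 0.9 carries over to the composite, and a two-sided two-sample t-test at 0.05 is used. Power comes from the noncentral t with 2n − 2 degrees of freedom and noncentrality d√(n/2). With b upper-limb blocks, n = (30 − 6b)/2 per arm.

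| Upper-limb blocks | Share of 30 | Per arm | Noncentrality | Power at d = 0.9 | d detectable at 80% power |
|---|---|---|---|---|---|
| 0 | 0% | 15 | 2.46 | 66.3% | 1.06 |
| 1 | 20% | 12 | 2.20 | 55.9% | 1.20 |
| 2 | 40% | 9 | 1.91 | 43.4% | 1.41 |

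One-sided, the powers are 77.6%, 68.8% and 57.3%.

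**5. Do the single-test comparisons rescue the upper-limb group?**

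DASH alone in one upper-limb block is 3 v 3, with a detectable d of about 3.1.

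**6. Precision of a within-limb SD**

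For six patients (5 degrees of freedom), the 95% interval for an SD runs from √(5/12.83) = 0.62 to √(5/0.831) = 2.45 times the estimate.

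**The case against.** The strongest reply is that the composite does not yet exist. Section 2.18 leaves its content open, so a score built on the three common evaluations, or standardised within limb, is still permitted. A reader might infer that upper-limb patients cannot be scored, or that the plan intends to drop them or to mix raw scales. The documents support neither reading; these are risks of an unstated rule. This part of the reply stands.

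Four further points stand in part.

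- With complete 3:3 blocks within limb, mixing scales adds noise and blurs meaning but does not bias the arm difference. An incomplete block would weaken that balance.
- Pooling raw score levels whose limb means lie an assumed 1 to 2 SD apart, with 20% upper-limb patients, multiplies the SD by √(1 + 0.2 × 0.8 × delta²). This shrinks d from 0.9 to 0.84 or 0.70 and power to 60% or 46%. A reader might take this as the expected loss. It is not: the gap is assumed, and Section 2.18 plans repeated measures analysis of change, from which a constant limb offset drops out.
- Section 3.12 foresees comparison within blocks, and Section 2.18 compares each test individually, so functional data are not lost. At 3 v 3, however, these comparisons cannot replace the composite for the upper limb.
- The composite is not named as a primary outcome in Section 2.17, and this is a pilot.

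None of this answers the within-patient problem. No rule keeps a patient's test set constant, and functional status may decide which tests are done.

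**Conclusion.** The point holds as a gap in the definition of the composite. There is no common-scale rule for the two limb levels, no limb term despite limb-based randomisation, and no fixed test set per patient. The third is the most serious, because test selection related to outcome can bias the arm comparison in a non-blinded trial. The limb mixture mainly costs precision and interpretability.

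The documents do not allow the size to be fixed. They give no effect size for the composite and do not set the number of upper-limb blocks; zero is possible, with no loss from this source. The fall from 66% to 56% or 43% illustrates only the case where upper-limb patients go unscored and d = 0.9 carries over. The bias from changing tests cannot be quantified from the documents.

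**What to change.** In Section 2.18, before arm-level data are seen, state that:

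1. The composite is each patient's mean standardised change from screening, with every test oriented so that higher is better. Standardise with the screening SD of that limb group, both arms pooled.
2. The test set is fixed at screening by limb level and the same set is used for scoring at months 6, 12 and 24.
3. A test in the fixed set that cannot be performed receives a score set in advance (for example, the worst score) rather than dropping out. This is a scoring rule and does not require the test to be attempted.
4. The arm comparison includes limb stratum.
5. The two limb groups are also reported separately, as description.
6. A sensitivity analysis uses only the evaluations common to both limbs, because an SD from about six upper-limb patients is very imprecise. Device-use history and physical examination need a stated numeric score before they can enter it.

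The cost is analysis-plan wording, simple scoring code, and alignment of the test-selection text in Sections 2.5.1 and 2.7 so that the fixed set is collected. No new instrument is needed. The downside is a score in SD units, which is less directly interpretable.

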45 CFR 46.406

The risk represents only a minor increase over minimal risk.

The research procedures present experiences to the subjects that are reasonably commensurate with those inherent in their actual or expected medical, dental, psychological, social, or educational situations.

The research procedures are likely to yield generalizable knowledge about the subjects' disorder or condition which is of vital importance for understanding or amelioration of the subjects' disorder or condition.

45 CFR 46.407

The risk is justified by the anticipated benefit to the subjects; and the relation of the anticipated benefit to the risk is at least as favorable to the subjects as that presented by available alternative approaches.

Provide a justification which must address all considerations related to the designated category of research:

[reviewer notes-]

3.6 Does this research study involve prisoners, or is it anticipated that the research study may involve prisoners?* No

3.6.1 The Federal Policy and FDA regulations specify that research involving prisoners must fall into one of the following permitted categories.

*

*Provide a justification for your designation:

General Requirements: The Federal Policy and FDA regulations specify that research involving prisoners must also conform to each of the following general requirements. Describe how your study meets each of the following regulations.

3.6.2 Any possible advantages accruing to the prisoner through his or her participation in the research, when compared to the general living conditions, medical care, quality of food, amenities, and opportunity for earnings in the prison are not of such a magnitude that the prisoner's ability to weigh the risks of the research against the value of such advantages in the limited choice environment of the prison is impaired. [45 CFR 46.305 (a)(2)]*

3.6.3 The risks involved in the research are commensurate with risks that would be accepted by nonprisoner volunteers.[45 CFR 46.305 (a)(3)] *

3.6.4 The procedures for the selection of subjects within the prison are fair to all prisoners and immune from arbitrary intervention by prison authorities or prisoners.[45 CFR 46.305 (a)(4)] *

3.6.5 Information regarding the research is presented to the potential prisoners-subjects in a language which is understandable to them.[45 CFR 46.305 (a)(5)]*

3.6.6 Adequate assurance exists that the parole boards will not take into account a prisoner's participation in the research in making decisions regarding parole, and each prisoner is clearly informed in advance that participation in the research will have no effect on his or her parole.[45 CFR 46.305 (a)(6)] *

3.6.7 Where there may be a need for follow-up examination or care of the prisoners-subjects after the end of their participation in the research, adequate provision has been made for such examination or care; taking into account the varying lengths of individual prisoners' sentences, and the prisoners have been informed of this fact. [45 CFR 46.305 (a)(7)]. *

[reviewer notes-]

Section 3 - Human Subjects

3.7 Will pregnant women be knowingly and purposely included in this research study?

* No

General Requirements: The Federal Policy [45 CFR 46, Subpart B] specify that research involving pregnant women and/or fetuses must also confirm to each of the following criteria. Describe how your study meets each of the requirements.

- 3.7.1 Where scientifically appropriate, preclinical studies, including studies on pregnant animals, and clinical studies, including studies on non-pregnant women, have been conducted and provide data for assessing potential risks to pregnant women and fetuses. [45 CFR 46.204 (a)] [Include references]*
- 3.7.2 The risk to the fetus is caused solely by interventions or procedures that hold out the prospect of direct benefit for the women or the fetus; or, if there is no such prospect of direct benefit, the risk to the fetus is not greater than minimal and the purpose of the research is the development of important biomedical knowledge which cannot be obtained by any other means. [45 CFR 46.204 (b)]
*
- 3.7.3 Any risk is the least possible for achieving the objectives of the research. [45 CFR 46.204 (c)]*
- 3.7.4 No inducements, monetary or otherwise, will be offered to terminate the pregnancy. [45 CFR 46.204 (h)]
*
- 3.7.5 Individuals engaged in the research will have no part in any decisions as to the timing, method, or procedures used to terminate a pregnancy. [45 CFR 46.204 (i)]
*
- 3.7.6 Individuals engaged in the research will have no part in determining the viability of a neonate.[45 CFR 46.204 (j)]

*

[reviewer notes-]

Section 3 - Human Subjects

